- 219 Vaccination with a live or attenuated vaccine within 28 days prior to day 1. Receipt of inactive/killed vaccinations (eg, inactive influenza) is allowed. Note

that receipt of the Th2 cytokine inhibitor suplatast within 15 days prior to randomization and during the study is not allowed.

- 220 Major surgery within 8 weeks prior to screening or planned inpatient surgery or hospitalization during the study period

Prior/Concurrent Clinical Study Experience

- 224 Currently receiving treatment in another investigational device or drug study, or less than 6 months since ending treatment on another investigational device or drug study(ies). Other investigational procedures while participating in this study are excluded.

Other Exclusions

- 225 Female subject is pregnant or breastfeeding or planning to become pregnant or breastfeed during treatment and for an additional **16** weeks after the last dose of investigational product. (Females of childbearing potential should only be enrolled in the study after a negative highly sensitive serum pregnancy test).
- 226 Female subjects of childbearing potential who are sexually active with unsterilized male partners unwilling to use 1 highly effective method of contraception during treatment and for an additional **16** weeks after the last dose of investigational product. Cessation of contraception after this point must be discussed with a responsible physician. Females of childbearing potential are defined as those who are not surgically sterile (ie, had bilateral tubal ligation, bilateral oophorectomy, or complete hysterectomy) or postmenopausal (defined as 12 months with no menses without an alternative medical cause). A highly effective method of contraception is defined as one that resulted in a low failure rate (ie, < 1% per year) when used consistently and correctly. Refer to [Appendix 5](#) for additional contraceptive information.
- 230 Subject has known sensitivity to any of the products or components to be administered during dosing.
- 231 History or evidence of any other clinically significant disorder, condition or disease (with the exception of those outlined above) that, in the opinion of the investigator or Amgen physician, if consulted, would pose a risk to subject safety or interfere with the study evaluation, procedures, or completion.

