9.2.4.2 Pregnancy Testing

[figure not shown]
A high sensitive serum pregnancy test should be completed at screening and a high sensitive urine test should be completed within 7 days of initiation of investigational product for females of childbearing potential. Therefore, for this study, the initial pregnancy tests will occur at screening and at the day 1 visit (which is within 7 days of initiation of investigational product).

Note: Females who have undergone a bilateral tubal ligation/occlusion should have pregnancy testing per protocol requirements. (If a female subject, or the partner of a male subject, becomes pregnant it must be reported on the Pregnancy Notification Worksheet, see [Figure 12-2](#)). Refer to [Appendix 5](#) for contraceptive requirements.

Additional pregnancy testing should be performed monthly during treatment with protocol-required therapies, then at week 52 and week 70 during the safety follow-up period.

If a urine pregnancy test is positive, a confirmatory serum pregnancy test will be performed and entered into the electronic case report form (eCRF).

[figure not shown]
Additional on-treatment pregnancy testing may be performed at the investigator's discretion or as required per local laws and regulations.

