Appendix 5. Contraceptive Guidance and Collection of Pregnancy and Lactation Information

Study-specific contraception requirements for male and female subjects of childbearing potential are outlined in [Section 6.2](#).

Female subjects of childbearing potential must receive pregnancy prevention counseling and be advised of the risk to the fetus if they become pregnant during treatment and for **16** weeks after the last dose of protocol-required therapies.

Additional medications given during the study may alter the contraceptive requirements. These additional medications may require female subjects to use highly effective methods of contraception and for an increased length of time. In addition, male subjects may also be required to use contraception. The investigator must discuss these contraceptive changes with the subject.

Definition of Females of Childbearing Potential

A female is considered fertile following menarche and until becoming postmenopausal unless permanently sterile. Permanent sterilization methods include hysterectomy, bilateral salpingectomy, and bilateral oophorectomy.

Females in the following categories are not considered female of childbearing potential:

- Premenopausal female with 1 of the following:
 - Documented hysterectomy;
 - Documented bilateral salpingectomy; or
 - Documented bilateral oophorectomy.

Note: Site personnel documentation from the following sources is acceptable:
1) review of subject's medical records; 2) subject's medical examination; or
3) subject's medical history interview.

- Premenarchal female
- Postmenopausal female
 - A postmenopausal state is defined as no menses for 12 months without an alternative medical cause. A high follicle stimulating hormone (FSH) level in the postmenopausal range may be used to confirm a postmenopausal state in women not using hormonal contraception or hormonal replacement therapy (HRT). However, in the absence of 12 months of amenorrhea, a single FSH measurement is insufficient.
 - Females on HRT and whose menopausal status is in doubt will be required to use 1 of the non-hormonal highly effective contraception methods if they wish to continue their HRT during the study. Otherwise, they must discontinue HRT to allow confirmation of postmenopausal status before study enrollment.

Contraception Methods for Female Subjects

Highly Effective Contraceptive Methods

Note: Failure rate of < 1% per year when used consistently and correctly.

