- Combined (estrogen and progestogen containing) hormonal contraception associated with inhibition of ovulation (oral, intravaginal, or transdermal)
- Progestogen-only hormonal contraception associated with inhibition of ovulation (oral, injectable, implantable)
- Intrauterine device (IUD)
- Intrauterine hormonal-releasing system (IUS)
- Bilateral tubal ligation/occlusion
- Vasectomized partner (provided that partner is the sole sexual partner of the female subject of childbearing potential and that the vasectomized partner has received medical assessment of the surgical success)
- Sexual abstinence (defined as refraining from heterosexual intercourse during the entire period of risk associated with the study treatments; the reliability of sexual abstinence must be evaluated in relation to the duration of the trial and the preferred and usual lifestyle of the subject)

Unacceptable Methods of Birth Control for Female Subjects

Birth control methods that are considered unacceptable in clinical trials include:

- Periodic abstinence (calendar, symptothermal, post-ovulation methods)
- Withdrawal (coitus interruptus)
- Spermicides only
- Lactational amenorrhea method

Collection of Pregnancy Information

Female Subjects Who Become Pregnant

- Investigator will collect pregnancy information on any female subject who becomes pregnant while taking protocol-required therapies through **16** weeks following the final administration of study drug.
- Information will be recorded on the Pregnancy Notification Worksheet (see [Figure 12-2](#)). The worksheet must be submitted to Amgen Global Patient Safety within 24 hours of learning of a subject's pregnancy. (Note: Sites are not required to provide any information on the Pregnancy Notification Worksheet that violates the country or regions local privacy laws.)
- After obtaining the female subject's signed authorization for release of pregnancy and infant health information, the investigator will collect pregnancy and infant health information and complete the pregnancy questionnaire for any female subject who becomes pregnant while taking protocol-required therapies through **16** weeks following the final dose of the study drug. This information will be forwarded to Amgen Global Patient Safety. Generally, infant follow-up will be conducted up to 12 months after the birth of the child (if applicable).

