- Any termination of pregnancy will be reported to Amgen Global Patient Safety, regardless of fetal status (presence or absence of anomalies) or indication for procedure.
- While pregnancy itself is not considered to be an adverse event or serious adverse event, any pregnancy complication or report of a congenital anomaly or developmental delay, fetal death, or suspected adverse reactions in the neonate will be reported as an adverse event or serious adverse event. Note that an elective termination with no information on a fetal congenital malformation or maternal complication is generally not considered an adverse event, but still must be reported to Amgen as a pregnancy exposure case.
- If the outcome of the pregnancy meets a criterion for immediate classification as a serious adverse event (eg, female subject experiences a spontaneous abortion, stillbirth, or neonatal death or there is a fetal or neonatal congenital anomaly) the investigator will report the event as a serious adverse event.
- Any serious adverse event occurring as a result of a post-study pregnancy which is considered reasonably related to the study treatment by the investigator, will be reported to Amgen Global Patient Safety as described in [Appendix 4](#). While the investigator is not obligated to actively seek this information in former study subjects, he or she may learn of a serious adverse event through spontaneous reporting.
- Any female subject who becomes pregnant while participating will discontinue study treatment (see [Section 8.1](#) for details).

Male Subjects With Partners Who Become Pregnant or Were Pregnant at the Time of Enrollment

- In the event a male subject fathers a child during treatment, and for an additional **16** weeks after discontinuing protocol-required therapies, the information will be recorded on the Pregnancy Notification Worksheet. The worksheet (see [Figure 12-2](#)) must be submitted to Amgen Global Patient Safety within 24 hours of the study center's awareness of the pregnancy. (Note: Sites are not required to provide any information on the Pregnancy Notification Worksheet that violates the country or regions local privacy laws.)
- The investigator will attempt to obtain a signed authorization for release of pregnancy and infant health information directly from the pregnant female partner to obtain additional pregnancy information.

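### Exclusion 226 and Appendix 5 classify tubal ligation and salpingectomy differently when defining childbearing potential, and 226 read with the schedule footnotes contradicts the pregnancy-testing Note in Section 9.2.4.2

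*Protocol*

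**What the plan says.** Two parts of the current protocol define who is of childbearing potential.

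- **Section 6.2, exclusion 226:** "Females of childbearing potential are defined as those who are not surgically sterile (ie, had bilateral tubal ligation, bilateral oophorectomy, or complete hysterectomy". Postmenopausal women are also outside the definition. The criterion then sends the reader to Appendix 5 for more on contraception.
- **Appendix 5, definition:** "Permanent sterilization methods include hysterectomy, bilateral salpingectomy, and bilateral oophorectomy". The list of premenopausal women who are not of childbearing potential repeats these three procedures, including "Documented bilateral salpingectomy; or". Tubal ligation is on neither list.
- **Appendix 5, contraceptive methods:** "Bilateral tubal ligation/occlusion" is listed among the highly effective methods.

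Pregnancy testing is governed in three places.

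- **Exclusion 225:** "Females of childbearing potential should only be enrolled in the study after a negative highly sensitive serum pregnancy test".
- **Table 2-1 footnote e and Table 2-2 footnote d:** scheduled pregnancy tests apply only to women of childbearing potential, with the protocol's own definition as the reference.
- **Section 9.2.4.2, Note:** "Females who have undergone a bilateral tubal ligation/occlusion should have pregnancy testing per protocol requirements".

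**The concern.** The footnotes rely on a protocol definition, but the protocol has two, and they disagree in both directions. A site that takes the definition from the eligibility section, which is a natural place to look, would class a woman with tubal ligation as sterile. The footnotes would then give it a reason not to test her.

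Test results drive decisions. Pregnancy excludes under 225, and Appendix 5 adds: "Any female subject who becomes pregnant while participating will discontinue study treatment". The opposite error is also possible: a woman with bilateral salpingectomy could be turned away under 226 although Appendix 5 regards her as permanently sterile.

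What is at stake is consistent pregnancy surveillance during exposure to an investigational antibody, and consistent application of one exclusion criterion.

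**Working it through.** No arithmetic applies. The check sets the texts side by side.

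**Step 1. Classify each procedure for a premenopausal woman.**

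| Procedure | Exclusion 226 | Appendix 5 |
|---|---|---|
| Hysterectomy | sterile | sterile |
| Bilateral oophorectomy | sterile | sterile |
| Bilateral tubal ligation | sterile | childbearing potential, using a highly effective method |
| Bilateral salpingectomy | not listed | sterile |

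This takes the complete hysterectomy of 226 and the hysterectomy of Appendix 5 as the same thing. The 226 list is introduced by *ie*, so on its face it is exhaustive, and a procedure left out does not count as sterility. The postmenopausal definitions agree: both use 12 months without menses and no other medical cause. The conflict is confined to the last two rows.

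**Step 2. Look for a rule of precedence.** Exclusion 226 refers to Appendix 5 for additional contraceptive information, not for the definition. Appendix 5 points back: "Study-specific contraception requirements for male and female subjects of childbearing potential are outlined in" Section 6.2. Each refers to the other, and neither is said to govern.

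**Step 3. Follow a woman with tubal ligation.**
- Testing under 226 with the footnotes: not of childbearing potential, so not tested.
- Testing under Appendix 5 with the footnotes: of childbearing potential, so tested.
- Testing under the 9.2.4.2 Note: should be tested, which agrees with Appendix 5.
- Eligibility under 226: not excluded on either definition. On the first she is outside the criterion. On the second she already has the one highly effective method that it asks for.

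**Step 4. Follow a woman with bilateral salpingectomy.**
- Under 226 read literally: of childbearing potential. She is excluded if she is sexually active with an unsterilized male partner and unwilling to use a highly effective method.
- Under Appendix 5: not of childbearing potential, so 226 does not apply.
- Section 6 allows no exceptions to the criteria, and Sections 6.4 and 9.1.1 bar rescreening of screen failures. A literal exclusion would therefore be final.

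**The case against.** The best argument on the other side is that Section 9.2.4.2, the section devoted to pregnancy testing, names exactly this group and says to test them. To omit the tests, a site would have to prefer a definition placed inside a contraception criterion over that instruction. Both schedule footnotes also allow extra testing when pregnancy is suspected. This largely stands: most sites would test.

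The Note does not remove the contradiction, however. It calls for testing in line with protocol requirements, and those requirements include the footnotes that exempt a woman who is sterile under 226. It also shows that the intent matches Appendix 5, which makes 226 the text to correct.

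On salpingectomy, the objection is that the case is narrow and errs on the cautious side, since the worst outcome is an unnecessary screen failure, and a site that follows the cross-reference will find the Appendix 5 rule. That is fair. It makes this half an eligibility matter rather than a safety risk.

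A reader might infer that women with ligation would go untested through the whole trial. The documents do not support that, because a site would have to disregard the Note at every scheduled visit. A reader might also infer that the conflict decides whether women with ligation may enroll. It does not decide this under 226 (Step 3), and pregnancy itself excludes under 225 on either definition.

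**Conclusion.** The inconsistency is real and stands in the current text. Two procedures, bilateral tubal ligation and bilateral salpingectomy, are classified differently by 226 and Appendix 5, and no rule says which text governs. For ligation, 226 combined with the schedule footnotes contradicts the Note in 9.2.4.2. For salpingectomy, a literal reading of 226 can exclude a woman whom Appendix 5 treats as sterile.

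The size is minor. The documents do not say how many women have had either procedure, so no count of missed tests or needless exclusions can be given. No endpoint, analysis set, error rate or power calculation is affected. The conclusion rests on reading the 226 list as exhaustive, and on taking the 9.2.4.2 Note and Appendix 5 as the sponsor's intent.

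**What to change.** In exclusion 226, delete bilateral tubal ligation from the examples of surgical sterility and add bilateral salpingectomy. Add one sentence stating that the Appendix 5 definition of childbearing potential is the single definition for exclusions 225 and 226, Table 2-1 footnote e, Table 2-2 footnote d and Section 9.2.4.2. Leave tubal ligation on the Appendix 5 list of highly effective methods, so that no woman with ligation loses eligibility under 226.

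The cost is a wording change. Under Appendix 3 an amendment must be submitted to the IRB/IEC and approved where necessary, so the change is best carried in the next amendment rather than prompting one of its own. It adds no visit, and no test beyond what 9.2.4.2 already expects. Appendix 5 asks that surgical sterility be documented, but it accepts a medical history interview as a source, so the added burden on sites is slight.

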6.3 Subject Enrollment

Before subjects begin participation in any study-specific activities/procedures, Amgen requires a copy of the study center's written institutional review board IRB/institutional ethics committee (IEC) approval of the protocol, informed consent form (ICF), and all other subject information and/or recruitment material, if applicable (see [Appendix 3](#)).

The subject or the subject's legally acceptable representative must personally sign and date the IRB/IEC and Amgen approved informed consent before commencement of study-specific procedures.

A subject is considered enrolled when the investigator decides that the subject has met all eligibility criteria. The investigator is to document this decision and date, in the subject's medical record and in/on the enrollment case report form (CRF).

Each subject who enters into the screening period for the study (when informed consent is signed) receives a unique subject identification number before any study-related activities/procedures are performed. The subject identification number will be assigned by IVRS/IWRS. This number will be used to identify the subject throughout the clinical study and must be used on all study documentation related to that subject.

The subject identification number must remain constant throughout the entire clinical study; it must not be changed after initial assignment.

This number will not necessarily be the same as the randomization number assigned for the study.

6.4 Screen Failures

Screen failures are defined as subjects who consent to participate in the clinical study but are not subsequently enrolled in the study. A minimal set of screen failure information will be collected that includes demography, screen failure details, eligibility criteria, medical history, prior therapies, and any serious adverse events.

Individuals who do not meet the criteria for participation in this study (screen failure) will not be rescreened.

7. Treatments

Study treatment is defined as any investigational product(s), non-investigational product(s), placebo, or medical device(s) intended to be administered to a study subject according to the study protocol.

Note that in several countries, investigational product and non-investigational product are referred to as investigational medicinal product and non-investigational medicinal product, respectively.

The Investigational Product Instruction Manual (IPIM), a document external to this protocol, contains detailed information regarding the storage, preparation, destruction, and administration of each treatment shown in [Table 7-1](#) below.

7.1 Treatment Procedures

7.1.1 Investigational Products

The amount of investigational product, total volume, quantity, dose start date/time, and box number are to be recorded on each subject's CRF.

Table 7-1. Study Treatments

Study Treatment Name	Amgen Investigational Product:^a	Placebo
Dosage Formulation	Each package will contain 3 vials.	Placebo will be presented in identical containers, and stored/packaged the same as tezepelumab.
Unit Dose Strength(s)/ Dosage Level(s) and Dosage Frequency	
Each subject will receive 3 injections per visit.
 
For subjects randomized to 420 mg SC Q2W, 280 mg SC Q2W, and 210 mg SC Q4W: volumes for injections from vials provided will be detailed in the Investigational Product Instruction Manual (IPIM).
 
Subjects randomized to Q4W dosing will receive placebo at intervening visits, such that all subjects receive an injection Q2W.
	
Each subject will receive 3 injections per visit.
 
For subjects randomized to placebo: volumes for injections from vials provided will be detailed in the IPIM.
 
Subjects will receive placebo dosing Q2W.

Route of Administration	SC injection	SC injection
Accountability	The amount of investigational product, total volume, quantity, dose start date/time, and box number of investigational product are to be recorded on each subject's CRF(s).	The amount of investigational product, total volume, quantity, dose start date/time, and box number of investigational product are to be recorded on each subject's CRF(s).
Dosing Instructions	
Investigational product will be administered by qualified study center personnel as the final activity for each study visit. The window for study visits is \pm 3 days.
 
Injection sites are to be rotated.
 
Subjects will be observed for 2 hours post-treatment at the day 1 and week 2 visits. For all other visits where investigational product is administered, subjects will be observed for a period of time at the discretion of the Investigator.
	
Investigational product will be administered by qualified study center personnel as the final activity for each study visit. The window for study visits is \pm 3 days.
 
Injection sites are to be rotated.
 
Subjects will be observed for 2 hours post-treatment at the day 1 and week 2 visits. For all other visits where investigational product is administered, subjects will be observed for a period of time at the discretion of the Investigator.

CRF = case report form; IPIM = Investigational Product Instruction Manual; SC = subcutaneous; Q2W = every 2 weeks; Q4W = every 4 weeks

^a Tezepelumab will be manufactured and packaged by Amgen and distributed using Amgen clinical study drug distribution procedures.

